7.2. Background

In 2011, the EU Pharmacovigilance Working Party (PhVWP) recommended that the product information for domperidone-containing medicines should be updated to reflect the risk of adverse cardiac effects of domperidone including QT prolongation, arrhythmias, and sudden cardiac death, and that domperidone should be used with caution in patients with certain heart conditions, including heart failure, a previous heart attack, angina (chest pains), and heart rhythm disorders. In response to this recommendation, the SmPC was updated in 2012 to include QT prolongation as an adverse drug reaction (ADR).

In March 2013, the EMA PRAC initiated a review of domperidone-containing medicines at the request of the Federal Agency for Medicines and Health Products (FAMHP), under Article 31 of Directive 2001/83/EC over concerns about cardiac adverse effects of domperidone. Subsequently, PRAC recommended that the product label (Summary of Product Characteristics/SmPC and Patient Information Leaflet/PIL) of domperidone-containing medicines should be updated to strengthen the information regarding cardiac risks. In addition, PRAC raised concerns that there may be off-label use of domperidone for the stimulation of lactation in breastfeeding women, for the treatment of

gastro-oesophageal reflux disease (GERD), for the treatment of diabetic and non-diabetic gastroparesis, and for the treatment of symptoms of postural hypotension in Parkinson's patients. More recently the EMA asked that IBS be included in the present study as an off-label indication.

The recommended changes following conclusion of the Article 31 referral included the following:

- restriction of the indication to nausea and vomiting;
- limitation of duration of use to 7 days;
- reduction of the maximum daily dose to 10 mg TID for adults and adolescents (12 years of age and older and weighing 35 kg or more);
- reduction of the maximum daily dose to 0.25 mg/kg TID for neonates, infants, children (less than 12 years of age), and adolescents weighing less than 35 kg;
- contraindication of the combination with other drugs that increase the cardiac risks by themselves or increase the plasma level of domperidone; and
- contraindication in patients with moderate or severe hepatic impairment or certain cardiac conditions.

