8.1. Primary Objectives

To describe the prescribing patterns before and after the changes to the domperidone label and distribution of a DHPC and estimate and compare the overall proportion of domperidone prescriptions before and after implementation of the risk minimisation measures regarding the following measures:

- Composite endpoint consisting of the following components:
 - Maximum daily dose;
 - Duration of use (>7 days);
 - Concomitant medications that prolong the QT-interval or are potent or strong CYP3A4 inhibitors;
 - Prescribing to patients with contraindicated conditions, e.g., moderate or severe liver disease, underlying cardiac diseases; and
 - Prescribing for off-label indications

Domperidone is used as needed, therefore the duration of use may not be the same as the number of days for which domperidone is supplied. As a result, duration of use will be assessed under the following 2 scenarios, which will be likely to bracket the actual (but unknown) situation:

- 1. Domperidone is used only for as little as 1 dose after it is prescribed, and
- 2. Domperidone is used for the entire number of days supplied.

This is intended to bracket the plausible values for duration of use

Primary test statistic: In each country studied, the change in the proportion of all prescriptions that comply with the label based on the above composite endpoint during the 12 months before the label change versus the 12 months after the label change is the primary statistic to be evaluated as a measure of the effectiveness of the label change in that country. The statistic will be evaluated as a risk ratio, i.e., as the ratio of the proportion of prescriptions that met all conditions in the composite endpoint between 1 April 2013 and 31 March 2014 and the proportion of prescriptions that met all conditions of prescriptions that met all conditions in the composite endpoint between 1 October 2014 and 30 September 2015. The point estimate and 95% confidence interval for the above risk ratio will be reported. There are several versions of the composite endpoint are implemented in the databases and the risk ratio (point estimate and 95% confidence interval) will be reported for each. Note that the term "risk ratio" is being used in the sense of a ratio of probabilities (the probability of a prescription being consistent with the new label).

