9.2.2. Study Period

The study period will be divided into a background period and pre- and post- implementation periods of risk minimisation measures as follows:

- A background period (1 January 2011 through 31 March 2013)
- A 1-year pre-implementation period of risk minimisation measures (1 April 2013 through 31 March 2014)
- A 1-year post-implementation period of risk minimisation measures (1 October 2014 through 30 September 2015)

The period during which the label change took place and the DHPC was sent will be used as the period during which the risk minimisation measures were implemented (1 April 2014 through 30 September 2014).

Because the amendments to the product information were suggested by the PhVWP in October 2011, the study will track prescribing pattern changes from 1 January 2011 (a time that preceded most of the discussion and implementation of the label changes, i.e., a background period) through 30 September 2015.

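### The primary pre/post ratio is read as the label change's effectiveness but cannot separate the 2014 measures from a trend already under way, up or down

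*Protocol*

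**What the plan says.** Section 8.1 of the protocol fixes one statistic per country: the ratio of the proportions of prescriptions meeting every condition of the composite in two one-year windows. The change it measures "is the primary statistic to be evaluated as a measure of the effectiveness of the label change in that country". On reporting, "The point estimate and 95% confidence interval for the above risk ratio will be reported", once for each version of the composite. No trend term, comparator or adjustment is attached.

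Section 9.2.2 sets the windows at 1 April 2013 to 31 March 2014 and 1 October 2014 to 30 September 2015, with the six months between them treated as the implementation period. It adds a background period from January 2011 to March 2013 and explains that "the study will track prescribing pattern changes from 1 January 2011". Section 9.7 calls the analysis descriptive and promises rates with 95% intervals for all endpoints in quarterly blocks over 2011-2015. Section 8.2 names time trends only for indication and days supplied.

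Section 7.2 describes regulatory activity before the first window: a 2011 recommendation on cardiac warnings, a 2012 SmPC update adding QT prolongation as an adverse reaction, and then "In March 2013, the EMA PRAC initiated a review of domperidone-containing medicines". Section 9.9.1 presents the before/after comparison as showing effectiveness. Section 9.9.2 does not mention secular trend.

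**The concern.** A ratio of two period averages measures change over time. It measures the effect of the 2014 measures only if compliance would otherwise have stayed level. The protocol's own background gives reasons to doubt that, and the 9 background quarters that could test it do not enter the statistic.

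The plan also contains a possible source of trend of its own. Section 9.3.4 searches for hepatic contraindications from a fixed 1 January 2011 up to the day before each prescription, so the look-back lengthens with calendar time and later prescriptions have longer to be flagged.

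At stake is the study's main conclusion in each country. An upward trend could be read as success of the label change, and a downward one could make working measures look ineffective.

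**Working it through.** The protocol gives no figure for a trend, so there is none to reproduce. The drift rates below are assumptions.

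**Inputs.** Windows from 8.1 and 9.2.2. (Section 9.7 ends the post window at 31 March 2015 while still calling it one year; that is a separate discrepancy, and the 8.1/9.2.2 dates are used here.) Sample size of 22,000 prescriptions per period, the Belgian 2015 count in 9.5, treated as eligible and independent. The ratio is taken as post over pre, so that values above 1 mean improvement, as in 9.5.

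**Gap between windows.** The midpoints are about 30 September 2013 and 1 April 2015: 18 months, or 6 quarters. A linear drift of d per quarter from pre-window compliance p, with no label effect, gives a crude ratio of (p + 6d)/p.

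| Pre-window compliance | d = 0.25 points | d = 0.5 points | d = 1 point |
|---|---|---|---|
| 10% | 1.15 | 1.30 | 1.60 |
| 30% | 1.05 | 1.10 | 1.20 |
| 50% | 1.03 | 1.06 | 1.12 |
| 70% | 1.02 | 1.04 | 1.09 |

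**Precision.** For 50% and 0.5 points per quarter: 0.50 + 6 × 0.005 = 0.53; z = 0.03/√((0.25 + 0.2491)/22,000) = 6.3; 95% CI 1.04 to 1.08. For 50% and 1 point: 1.12 (1.10 to 1.14). For 10% and 0.25 points: 1.15 (1.09 to 1.21). In relative terms, 1.016⁶ = 1.10, so a drift of 1.6% per quarter alone reaches the ratio below which 9.5 considers improvements of limited interest.

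**Masking.** A true 3-point step from 50% with a drift of -0.5 points per quarter gives 0.50 + 0.03 - 6 × 0.005 = 0.50, a crude ratio of 1.00. Against the projected 0.47 the ratio is 0.50/0.47 = 1.06.

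**Can the planned data separate the two?** There are 9 + 4 = 13 quarters before implementation and 4 after. With 5,500 prescriptions per quarter (22,000/4), a straight-line drift and no label effect, comparing the post mean with the line projected from the 13 quarters gave an average ratio of 1.00, significant in about 5% of simulated studies. The crude ratio was significant in about 100% of them.

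**Limit of a single slope.** That result holds because the simulated trend was the straight line being projected. Suppose instead that compliance is flat at 50% to Q1 2013 and then rises 0.5 points per quarter. The window means are 0.5125 and 0.5425, a crude ratio of 1.059. A log-link model with one linear slope, season and a level change returns 1.044 (1.02 to 1.07). On the log scale ln(1.044)/ln(1.059) is about 0.75, so three quarters of the bias remains.

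**Look-back.** The hepatic look-back from 1 January 2011 runs from 27 to 39 months across the pre window and from 45 to 57 months across the post window. It is near zero in early 2011, where a long trend line would begin.

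**Cost in precision.** Under independence, the standard error of the log ratio from the single-slope model is about 0.013 against 0.0095 for the crude ratio at 50%, and 0.039 against 0.029 at 10%: about one third larger.

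**The case against.** The study calls itself descriptive, and the checklist in Annex 2 says that no formal hypothesis is tested. Quarterly rates with intervals will be reported alongside the ratio, so a reader could see a trend. The amendment table in section 5 records that the comparison was added at the regulator's request. The size and direction of drift are wholly assumed, and the 1.06 example lies below the 1.1 that section 9.5 treats as worth detecting. Any reaction to the March 2013 review would fall inside the pre window, raise the baseline and pull the ratio towards 1. The 2012 update concerned an adverse reaction, and so gives weak grounds for drift in dose, duration or indication. Finally, a trend model can itself mislead.

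Much of this stands. A reader might infer that the plan credits any ongoing trend to the label change, or declares success when the interval excludes 1. The documents do not support that: there is no such decision rule, and the quarterly series is to be shown. Nor do they show that the ratio is inflated, since bias could run either way. The z values are also upper bounds, because the count is not filtered for eligibility and repeat prescriptions within a patient are correlated.

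What remains is that section 8.1 itself reads the ratio as effectiveness. Describing the analysis as descriptive does not remove that reading, and nothing says how the quarterly series should qualify it.

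**Conclusion.** The point holds as a weakness of interpretation: the crude ratio cannot tell the 2014 measures from a trend already under way, and the plan does not use its 2011-2015 series to inform the effectiveness statement. Bias is possible, not shown. Under assumed drifts of 0.25 to 1 point per quarter with no label effect, the three cases worked with intervals give ratios of 1.06 to 1.15; the full grid runs from 1.02 (70%, 0.25 points) to 1.60 (10%, 1 point). A downward drift hides a real effect to a similar degree. These figures assume linear drift, and the intervals assume 22,000 independent eligible prescriptions per period. Season is roughly balanced, because both windows in 8.1 and 9.2.2 cover a full year. A further inference, that one straight line through all pre-implementation quarters would settle the matter, also fails if the trend changed around March 2013.

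**What to change.** Keep the crude ratio in 8.1 as the regulator-requested pre/post comparison, and add the following to 8.1 and 9.7:

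- A per-country segmented (interrupted time-series) log-link model of the quarterly composite, omitting April to September 2014, with linear time, season and a level change at 1 October 2014. Standard errors should allow for repeat prescriptions within patients and for overdispersion.
- A prespecified sensitivity analysis in which the pre-implementation slope may change around the March 2013 review.
- A hepatic look-back of equal length for all quarters, or a later start to the series, so that look-back length does not create a trend.
- For Spain, where Annex 5 dates specialist data from 2012, a start once specialists are included, or restriction to general practitioners.
- An interpretation rule: call the change an effect of the label change only when the crude and trend-adjusted results agree; otherwise report it as a change over time.

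Add secular trend to the limitations in 9.9.2.

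The model uses the quarterly data already planned. The costs are an interval about one third wider under independence (wider again in the sensitivity analysis), only 4 post-implementation quarters, so that the level change is better determined than any change in slope, and dependence on the assumed trend shape.

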8.2. Secondary Objectives

To estimate the overall proportion of domperidone prescriptions before and after implementation of the risk minimisation measures for domperidone for each of the components of the composite endpoint individually, the time trend of apparent indication, and days supplied (\leq 7 days vs. >7 days), and the age and sex of the people receiving prescriptions.

9. **RESEARCH METHODS**

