9.3. Variables

9.3.1. Demographic Characteristics

Information on patients' age, sex, and geographic region will be extracted. Diagnoses will be extracted from a read codes (CPRD), ICD codes, or will be determined based on laboratory test results.

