10.1 Does the plan include measurement of excess risks?				
10.2 Is the choice of statistical techniques described?	\boxtimes			16,17
10.3 Are descriptive analyses included?	\boxtimes			19,21
10.4 Are stratified analyses included?	\boxtimes			7,14
10.5 Does the plan describe methods for adjusting for confounding?			\boxtimes	

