10.6 Does the plan describe methods addressing effect modification?				

This is a drug utilisation study examining the extent and patterns of drug use. Therefore, the analysis planned for the study is descriptive in nature. Results are stratified by country.

Section 11: Data management and quality control	Yes	No	N/A	Page Number(s)
11.1 Is information provided on the management of missing data?			\square	
11.2 Does the protocol provide information on data storage? (e.g. software and IT environment, database maintenance and anti-fraud protection, archiving)	\square			21,22
11.3 Are methods of quality assurance described?	\square			21,22
11.4 Does the protocol describe possible quality issues related to the data source(s)?		\boxtimes		

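### The pre/post ratio is read as the effect of the label change with no companion estimate at constant age-sex mix, although age and sex are already extracted

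*Protocol*

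**What the plan says.** Section 8.1 defines the primary statistic, country by country, as a ratio of two proportions: compliant prescriptions from 1 April 2013 to 31 March 2014, and from 1 October 2014 to 30 September 2015. This ratio "is the primary statistic to be evaluated as a measure of the effectiveness of the label change in that country". For each version of the composite, "The point estimate and 95% confidence interval for the above risk ratio will be reported". No stratification or standardisation within country is named in 8.1 or 9.7.

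In Annex 2, the checklist item "10.5 Does the plan describe methods for adjusting for confounding" is marked not applicable. The comment to that checklist section reads: "Therefore, the analysis planned for the study is descriptive in nature. Results are stratified by country".

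The variables are at hand. Section 9.3.1 states: "Information on patients' age, sex, and geographic region will be extracted". Their planned uses are descriptive:
- section 8.2 lists "the age and sex of the people receiving prescriptions" among the secondary items;
- section 9.7 adds a demographic table, not stated to be split by period, and a separate description of children.

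The compliance definition refers to both variables. The dose criterion takes a different form below and from 12 years (9.3.6), and below 12 it needs a recorded weight (9.3.3). Lactation problems are one of the off-label indications (9.3.2).

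**The concern.** The two periods contain different prescriptions, and their midpoints are 18 months apart (1 October 2013 and 1 April 2015). Nothing in the design holds the patient mix constant. If compliance differs between age-sex groups, the overall proportion is a weighted average whose weights can change without any prescriber treating a given kind of patient differently.

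This is distinct from a time trend in compliance, because it arises even when compliance in every group is flat. What is at stake is the effectiveness statement. A crude ratio away from 1 may reflect better label adherence for similar patients, a different set of patients, or both, and the primary result alone does not separate them. A mix shift in the other direction can also hide a real improvement.

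**Working it through.** The plan gives no compliance by age or sex and no expected mix shift, so there is no figure of its own to reproduce on this point. Two of its numbers (section 9.5) serve as anchors: 22,000 prescriptions in the smallest database (Belgium, 2015 count), and a ratio of 1.1, below which improvements are said to be of limited interest. Ratios here are post over pre, as in 9.5.

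**Assumed inputs.** Compliance 60% in children, 50% at 18-64 and 30% at 65+, identical in both years. Pre-period mix 20/50/30%. 22,000 independent prescriptions in each year.

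**Formulas.** p = Σ share × group compliance; RR = p1/p0; SE(log RR) = √[(1−p0)/(22,000·p0) + (1−p1)/(22,000·p1)]; 95% CI = RR × exp(±1.96·SE).

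**Base.** p0 = 0.20×0.60 + 0.50×0.50 + 0.30×0.30 = 0.460.

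**5 points from 65+ to children.** p1 = 0.25×0.60 + 0.50×0.50 + 0.25×0.30 = 0.475. RR = 0.475/0.460 = 1.033. SE = √(0.54/10,120 + 0.525/10,450) = 0.0102. CI 1.012-1.053.

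| Scenario | p0 → p1 | RR (95% CI) |
|---|---|---|
| 5 points, 65+ to children | 0.460 → 0.475 | 1.033 (1.012-1.053) |
| 5 points, children to 65+ | 0.460 → 0.445 | 0.967 (0.948-0.987) |
| 10 points, 65+ to children | 0.460 → 0.490 | 1.065 (1.044-1.086) |
| Weaker gradient 50/45/35%, 5 points to children | 0.430 → 0.4375 | 1.017 (0.996-1.039) |
| First row, design effect 2 for repeat prescriptions (assumed) | 0.460 → 0.475 | 1.033 (1.004-1.062) |

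In every row a ratio standardised to the pre-period mix is exactly 1.00, because group compliance was held constant.

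**How large a shift excludes 1.** With two strata and overall compliance of 50%, the critical difference is 1.96 × √(2×0.5×0.5/22,000) = 0.0093. Dividing by the compliance gap between strata gives a shift of 9.3, 4.7 or 3.1 points for gaps of 10, 20 or 30 points. With a design effect of 2 these become 13.2, 6.6 and 4.4 points. A 2-point shift between strata at 60% and 40% (half in each at the start) gives 1.008 (0.989-1.027), which is not distinguishable from 1.

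**Against the plan's threshold of 1.1.** In the three-group model, 1.1 needs p1 = 1.1 × 0.460 = 0.506, a rise of 0.046. Each point moved from 65+ to children adds 0.003, so about 15 of the 30 points must move. At low compliance less is needed: strata at 20% and 8%, with the first stratum's share going from 20% to 30%, give 0.116/0.104 = 1.115 (1.058-1.176).

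**Masking.** If every group truly improves by a factor of 1.10, a 5-point shift to 65+ gives a crude ratio of 1.10 × 0.445/0.460 = 1.064.

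**The case against.** The strongest objection is that much of the label change concerns who should receive the drug: the indication, contraindicated conditions and contraindicated co-medication. If prescribers stop starting older cardiac patients or women with lactation problems, the age-sex mix changes because the label worked, and standardisation would remove that success. This stands. A reader might infer that the effectiveness statement should rest on the standardised ratio alone, or that the gap between the two ratios measures the label-driven part. Neither follows, because the gap mixes label-driven and unrelated change in mix.

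Second, the study calls itself descriptive, and a crude population proportion is a defensible target. That is a reason to keep it as the primary statistic. It does not cover the effectiveness reading that 8.1 attaches to it.

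Third, the magnitudes rest on assumed gradients and independent prescriptions. This also stands. Patients can contribute repeat prescriptions, and the 5-point result (z about 3.15) loses significance at a design effect above (3.15/1.96)² ≈ 2.6. The 22,000 is not stated to be net of the 180-day history requirement. That contraindicated conditions and co-medications cluster in older patients is an assumption, and a dose rule that changes form at 12 does not by itself show that compliance differs by age.

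Fourth, the mix is not ignored. The secondary description of age and sex, the separate paediatric description, the quarterly rates and the component comparisons may reveal a material shift, and two full calendar years balance seasonal mix. These displays can show a shift, but none tells the reader what the ratio would be without it.

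Finally, standardised supporting estimates often belong in a statistical analysis plan, and the not-applicable mark does not forbid one. But the protocol itself fixes the effectiveness reading and declares adjustment inapplicable, so its text needs the change.

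**Conclusion.** The point holds as a recommended addition. Section 8.1 reads an unadjusted ratio as effectiveness and the checklist rules adjustment inapplicable, while age and sex are available and the compliance rules refer to them. Mix alone can move the ratio: under the stated assumptions by about 2 to 7% for shifts of 5 to 10 points, in either direction. Whether the interval excludes 1 depends on the gradient, the size of the shift and the clustering of prescriptions within patients, none of which the documents give.

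A reader might infer that the primary ratio is invalid, or that a mix shift would by itself produce an improvement the plan would call relevant. The documents support neither. The crude ratio validly describes actual prescribing. Most mix-only ratios fall below 1.1; the one case worked here that exceeded it needed compliance of 20% and 8% in the two strata and a 10-point shift.

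**What to change.** In sections 8.1 and 9.7:
- keep the crude ratio as the primary statistic;
- beside it, for each country and each version of the composite, report a ratio standardised to the pre-implementation distribution of age group by sex;
- show the demographic table separately for the pre and post years;
- interpret effectiveness from both ratios, stating that a difference between them reflects change in patient mix, which may be partly caused by the label and partly unrelated to it, and that standardisation does not remove a secular trend.

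Align checklist item 10.5 and its comment with this.

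The cost is one more estimate per table, from variables already extracted, plus a short wording change. The downside is that the standardised ratio excludes any label effect that acts through the age-sex mix, which is why it accompanies the crude ratio and does not replace it.
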